## Study groups -

**Group 1**: Low dose 50 mg/kg given two times a day for a total of 7 days (100 mg/kg/day) **Group 2**: Medium dose 100 mg/kg given two times a day for a total of 7 days (200 mg/kg/day)

**Group 3:** High dose 150 mg/kg given two times a day for a total of 7 days (300 mg/kg/day)

**Justification for dosing:** Pharmacokinetic studies show that half-life of IV citrulline is 60 minutes(8). Half-life of enteral Citrulline has not been studied but previous studies by Montogemery et al, Schwedhelm et al and Waugh et al reported efficacy with twice daily dosing(3, 6, 9). We will also use twice daily dosing. The actual dosing used in previous studies were 80 mg/kg twice daily and 100 mg/kg twice daily respectively. Study in newborn piglets shows that higher doses are associated with greater efficacy. We will use three different dose ranges to determine efficacy (i.e. plasma citrulline level > 37 μmol/L. increase in plasma arginine levels and urinary nitrites/nitrates).

### 5.0 Study Procedures

**Data collection** - Antenatal, delivery & post-natal (after birth), all detailed data will be collected from electronic medical records (EMR) by the investigators & saved in a password protected computer. We will calculate SNAPPE 2 (Score for Neonatal Acute Physiology – Perinatal Extension 2 – a 9 point validated scoring system that predicts neonatal mortality(10)) for all subjects to ensure equal distribution of sick infants.

**Study drug** – Oral/enteral L-Citrulline as 10 % solution (100 mg/ml) will be provided to the bedside nurse by the Investigational Pediatric Pharmacy. The drug will be given via gavage feeding by bolus infusions followed by a 0.5 ml water flush twice daily (1200 and 0000). Bolus dosing will be needed due to the small volumes (0.5–1.5 ml per dose in most infants). The volume of nasogastric tubing used in preterm infants (Ameritus 4.0 Fr 50 cm) is 0.48 ml, therefore we will follow the administration with 0.5 ml of saline/water flush to ensure all the study drug is delivered to the patient.

Dispensing study drug - After enrollment & randomization, the research nurse will inform the pharmacy about randomization group. A 10% solution of L-citrulline will be prepared to administer 50 mg/kg, 100 mg/kg and 150 mg/kg doses for Groups 1,2 and 3 respectively. The shelf life of dispensed L-citrulline is 24 hours. L-citrulline will be dispensed as a single dose twice daily for each subject.

Administration of study drug - Will be given via gavage feeding tube twice daily (1200  $\pm$  30 mins, 0000  $\pm$  30 mins). The time of 0000 will be in the window of citrulline's peak serum levels at 5-8 hours when routine blood collection is done at 0400(11). L-citrulline will be given by the bedside nurse as a bolus followed by 0.5 ml water flush. L-citrulline will be given separate from feeds to avoid any confusion.

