### 4.0 Treatment Assignment/Randomization

**Recruitment** - Parents of all eligible infants will be approached by research investigator to discuss about the study & research protocol in detail. All questions & concerns will be answered in very simple language & parents will be given written consent form to read. Within 24 to 48 hours, the parents will be approached again to discuss & explain any question they have. We expect around 70 - 75% success in the recruitment. Every year, we deliver around 50 infants ( $\leq$ 30 weeks' gestation). We hope to recruit our desired sample of 42 infants (14 in each study group) within 12 months.

**Sample size:** 14 preterm infants will be randomized to each group (total sample 42) A sample size of 14 at each group (low, median, and high dose) for efficacy endpoint will reach a power of 0.80 to detect an effect size of 0.5 based on one-way ANOVA with a 0.05 significance level. A sample size of 11 at each group for safety endpoint will reach a power of 0.92 at a 0.05 significant level for an equivalence test of means using two onesided tests, when the true difference between the means is 0.0 mmHg, the standard deviation is 10.0 mmHg, and the equivalence limits are -15.0 mm Hg and 15.0 mmHg.

**Randomization:** Adaptive randomization method will be used – each new participant will be sequentially assigned to a particular treatment group by taking into account the previous assignments of participants. For example, first recruit will be Group 1, second Group 2, third Group 3, fourth Group 1 and so on. The study will be blinded to the nurses and parents. If patients complete 12/14 doses of the treatment, they will be analyzed in the treatment arm.

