# Procedure for accounting for any missing, unused and spurious data:

In this pilot study, subjects with missing data on important predictors (lack of blood sample for serum arginine/citrulline levels) will be excluded from analyses.

Selection of subjects to be included in the analyses:

We will follow an intention-to-treat approach in the analyses. The primary variables (plasma arginine, citrulline levels and urinary nitrite, nitrate levels) are continuous data

and the one-way ANOVA will be used to analyze differences amongst the 3 treatment groups from day 0 and day 7. Paired T-test will be used to evaluate differences pre-and post-treatment in individual subjects. The data gathered from daily urinary nitrite and nitrate measurements will be represented in line graphs to represent the trend.

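### SNAPPE 2 is collected to secure balance in illness severity, but neither the assignment rule nor the between-dose analysis uses it, so that balance is not ensured

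*Combined protocol and SAP*

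**What the plan says.** Under Data collection, section 5.0 describes SNAPPE 2 as a "validated scoring system that predicts neonatal mortality" and says it is calculated "for all subjects to ensure equal distribution of sick infants". Apart from its source in the reference list, the score is not mentioned again in the text available for review.

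Section 4.0 calls the allocation adaptive. The rule is that "each new participant will be sequentially assigned to a particular treatment group by taking into account the previous assignments of participants", and the example is that the "first recruit will be Group 1, second Group 2, third Group 3, fourth Group 1 and so on". No infant characteristic enters the rule.

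Section 9.0 says that "the one-way ANOVA will be used to analyze differences amongst the 3 treatment groups from day 0 and day 7" and that a "Paired T-test will be used to evaluate differences pre-and post-treatment in individual subjects". It also lists linear models, repeated measures ANOVA and logistic modelling in general terms, without naming a covariate, a stratum or a baseline comparison of SNAPPE 2.

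**The concern.** The protocol gives the score a job, equal distribution of sick infants across the dose groups, and then provides nothing that could do it. A score affects balance only if it enters the allocation. It corrects a comparison for imbalance only if it enters the analysis. Here it does neither.

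The gap is separate from the predictability of the 1-2-3 rotation. A concealed random list would cure that, but would still not secure the severity balance that section 5.0 states.

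The protocol's own background gives some reason to care. It treats arginine as essential under stress, infection and prematurity, and places citrulline production in the gut and its conversion to arginine in the kidney. Hypotension is the main named safety concern. A reader who is told that sickness was equally distributed could credit a difference between doses wholly to dose when part of it reflects severity. That severity influences these outcomes is an inference; the documents link SNAPPE 2 only to mortality.

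**Working it through.** **1. The texts side by side.**

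| Step | What it uses | Role of SNAPPE 2 |
|---|---|---|
| Purpose (section 5.0) | Score calculated for each infant | Said to secure equal distribution |
| Assignment (section 4.0) | Earlier assignments only | None |
| Between-dose test (section 9.0) | Dose group, one-way ANOVA | None |
| Within-infant test (section 9.0) | Day 0 and day 7 values | None |

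The rotation equalises group counts, not group severity.

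**2. The plan's own power figure.** Inputs from sections 4.0 and 9.0: 3 groups of 14 (N = 42), effect size f = 0.5, alpha 0.05. Noncentrality = N × f² = 42 × 0.25 = 10.5, with 2 and 39 degrees of freedom. Power from the noncentral F distribution is 0.803, against 0.80 stated. The figure reproduces and is not in dispute.

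**3. Chance imbalance in the score.** Assumptions: assignment unrelated to severity, and an approximately normal score measured in SD units.

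- One pair of groups: the SE of the difference is √(2/14) = 0.378 SD. P(gap > 0.5 SD) = 2 × [1 − Φ(0.5/0.378)] = 0.19.
- Largest of the three pairwise gaps, by simulation: P(> 0.5 SD) = 0.38, P(> 0.75 SD) = 0.12, median 0.42 SD.
- Expected largest gap: the mean range of three standard normals is 1.693, and 1.693/√14 = 0.45 SD.

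**4. From score to outcome.** An imbalance in the score shifts an outcome contrast by roughly gap × correlation, in outcome SDs. The documents give no correlation, so 0.2 and 0.5 are assumed. Section 9.0 expects citrulline SDs of 4–5 μmol/L.

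| Gap (SD) | Assumed correlation | Shift (SD) | Shift (μmol/L) |
|---|---|---|---|
| 0.45 | 0.2 | 0.09 | 0.36–0.45 |
| 0.75 | 0.5 | 0.375 | 1.5–1.9 |

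The expected low-to-high difference in section 9.0 is 45 − 19 = 26 μmol/L, so either shift is small against it. Against f = 0.5 the shift weighs more. If the three means are equally spaced, f = 0.5 puts the outer two 2 × 0.5 × √1.5 = 1.22 SD apart, and the shifts are 0.09/1.22 = 7% and 0.375/1.22 = 31% of that.

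**5. Effect of using the score as a covariate.** Error degrees of freedom fall from 39 to 38, and the noncentrality becomes 10.5/(1 − r²).

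| Assumed correlation r | Noncentrality | Power |
|---|---|---|
| No covariate | 10.5 | 0.80 |
| 0 | 10.5 | 0.80 |
| 0.2 | 10.9 | 0.82 |
| 0.3 | 11.5 | 0.84 |
| 0.5 | 14.0 | 0.91 |

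The formula ignores the small loss from chance imbalance in the covariate itself. Simulating the adjusted test with that included (40,000 trials per value of r, equally spaced means) gives 0.79, 0.81, 0.83 and 0.90 for r = 0, 0.2, 0.3 and 0.5. The conclusion is the same, about 0.01 lower throughout.

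**The case against.** The strongest reply is that the sentence is loose wording for a baseline check in a small single-centre pilot, and that the harm is limited. Much of this stands.

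- **Eligibility narrows severity.** A reader might infer that every infant of 30 weeks or less is dosed, so severity ranges without limit. Section 3.0 excludes anomalies, relevant heart disease, and NEC, sepsis or a surgical condition before recruitment. Section 5.0 delays the drug until the infant has been off TPN for at least 3 days. How far this narrows the range is not stated.
- **Some comparisons are protected.** A reader might infer that nothing in the plan deals with differences between infants. The paired tests use each infant as its own control and remove stable differences. The ANOVA wording may also mean change from day 0, though it is unclear. Neither adjusts the between-dose contrast for a response that depends on severity, and the pre-post biochemical tests do nothing for the hypotension comparison.
- **Chance imbalance is not bias.** A reader might take the 38% as the chance of a wrong dose conclusion. It is not. If assignment is unrelated to severity, the unadjusted ANOVA keeps its error rate, and omitting a prognostic score costs precision. Systematic bias would have to come from the predictable rotation, which is a different point.
- **Linear models are listed.** That leaves room for a covariate, but room is not a specification.

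What does not stand is the sentence itself. Even read charitably, checking a score does not ensure its distribution, and section 9.0 does not plan the check.

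**Conclusion.** The point holds in a limited form. The protocol states a property, equal distribution of sick infants, that its assignment rule does not secure, and it collects a severity score that its between-dose analysis does not use. It is tempting to say that the groups will be unbalanced. The documents do not support that: balance may arise by chance, and the exact statement is that it is not ensured.

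The size, with 14 per group, is a probability of about 0.38 that some pair of groups differs by more than 0.5 SD in mean SNAPPE 2, and an expected largest gap of about 0.45 SD. This rests on a roughly normal score and assignment unrelated to severity. The consequence for citrulline, NO products or blood pressure cannot be fixed from the documents, because no score-outcome correlation is given. For citrulline, over the assumed range, it is small against the expected 26 μmol/L difference but not negligible against f = 0.5. The change is worth making because the statement is inaccurate and the correction is cheap, not because the dose comparison is shown to be invalid.

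**What to change.** 1. **Section 9.0:** prespecify SNAPPE 2 as a covariate in the between-dose model for the continuous outcomes, and state that it enters as a single linear term.
2. **Section 9.0:** report SNAPPE 2 by dose group as a baseline summary.
3. **Section 5.0:** change the stated purpose to *to describe and adjust for severity of illness*, and say when the score is taken. As a covariate it must be fixed before the first dose, and the text gives no timing.

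The cost is one of 39 error degrees of freedom and a few lines of text. No new data are needed, since the score is already planned for every infant. If the score proves unrelated to the outcome, the loss of power at f = 0.5 is about 0.01 at most.

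Balancing on SNAPPE 2 in the allocation is optional. It is a debatable choice for 42 infants, is possible only if the score is available before assignment, and belongs with any revision of the rotation in section 4.0. Covariate adjustment corrects for imbalance and does not create balance, which is why the wording in section 5.0 has to change with it.

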## Dose of study drug -

Low dose 100 mg/kg/day Medium dose 200 mg/kg/day High dose 300 mg/kg/day

[figure not shown]
**When to start study drug -** Study drug will be started when infant has been off of TPN for at least 3 days so that IV arginine in TPN does not interfere.

**Sample collection** - 1 mL of blood will be collected from each subject at 2 time points: before starting citrulline (Day 0) and then after completing 1 week enteral L-citrulline supplementation (Day 7). Discarded blood sample from routine blood draw will be used.

It is standard of care for all preterm infants to get weekly blood draws on Tuesdays for hemoglobin monitoring. We will use discarded blood sample from the Tuesday after being on full feeds (no TPN) and start enteral L-citrulline supplementation on the first Tuesday (Day 1) after off TPN for at least 3 days. After 1 week, supplementation will be discontinued (last dose Monday PM) and discarded blood sample from Tuesday (Day 7) will be used to analyze plasma levels or L-citrulline and L-arginine. Immediately after blood collection, blood will be centrifuged at 4-degree C to extract serum. Serum will be divided into aliquots of 100 microliter & stored at -80-degree C for future use.

1 mL of urine will be collected before starting (Day 0) and then daily thereafter till the last day of L-citrulline supplementation (Day 7). Urine will be collected by placing cotton balls in diapers at around noon  $\pm$  2 hours (in between the 2 doses of study drug).

All sample collection will be part of routine/standard care of the infant and no extra blood draws/invasive procedures will be needed.

Sample collected - (time points)

- \*Discarded blood (for arginine, citrulline & ADMA)
- ^Urine daily for urinary arginine, citrulline, nitrites and nitrates

**\*Enteral L-citrulline** –low, medium or high dose divided into 2 doses via gavage feeding tube i.e. 10% L-citrulline twice daily.

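### The 0400 blood draw falls 4 h after the midnight dose, outside the plan's own 5–8 h peak window, and the noon urine window is centred on a dose rather than between doses

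*Combined protocol and SAP*

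**What the plan says.** Section 5.0 schedules the study drug "twice daily (1200 and 0000", with a tolerance of 30 minutes either way. In the paragraph on administration it justifies the midnight dose by linking it to "peak serum levels at 5-8 hours when routine blood collection is done at 0400".

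The sample collection text in the same section plans two blood samples per infant, one before treatment and one after a week. Both are left over from routine Tuesday draws. Urine is collected before treatment and then "daily thereafter till the last day of L-citrulline supplementation (Day 7", at noon ±2 h, which is described as "in between the 2 doses of study drug".

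On day labels, the plan will "start enteral L-citrulline supplementation on the first Tuesday (Day 1"), and a week later the "discarded blood sample from Tuesday (Day 7) will be used to analyze plasma levels".

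Section 9.0 makes plasma citrulline and urinary nitric oxide products the primary outcome. Day 0 and Day 7 values go into a one-way ANOVA and paired t-tests, and the daily urine values are shown as line graphs. Specific Aim 3 seeks the dose that brings citrulline above 37 µmol/L.

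**The concern.** The plan gives a reason for each sampling time, and neither reason agrees with its own dosing clock. This matters most for plasma because each infant has only one on-treatment blood sample. The citrulline part of the primary outcome and the >37 µmol/L dose-finding result both rest on it. If readers take that value as a peak level, the plan's own figures contradict them.

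For urine, staff cannot follow both halves of the instruction. Noon is when a dose is given, so a sample taken then is either just before a dose or just after one. Two infants sampled correctly under the protocol on the same day may be at opposite ends of the dosing interval. That adds scatter to the daily nitrite and nitrate trend, and the stated aim of a between-dose sample is not met on any day.

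**Working it through.** **Inputs.** All come from section 5.0: doses at 1200 and 0000 (±0.5 h), blood at 0400 (no tolerance stated), claimed peak at 5–8 h, urine at 1200 ±2 h (1000–1400). Section 4.0 gives two doses a day for 7 days, which is 14 doses.

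**Last dose.** The pre-treatment blood comes from a Tuesday draw. I assume the first dose follows it at 1200 that day. Dose 14 is then 13 × 12 = 156 h later, which is 6.5 days, at midnight between Monday and Tuesday.

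**Plasma: can the 5–8 h figure be reproduced?**
- From the 0000 dose: 4 − 0 = 4 h. With the tolerance, 4 − 0.5 = 3.5 h to 4 + 0.5 = 4.5 h.
- Shortfall from 5 h: 5 − 4.5 = 0.5 h to 5 − 3.5 = 1.5 h, nominally 1 h.
- From the preceding 1200 dose: 4 + 12 = 16 h, also outside 5–8 h.
- Reading 5–8 as clock hours gives 0500–0800, which still excludes 0400.

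No reading reproduces the claim at the stated times. A late draw at 0430 after an early dose at 2330 would just reach 5 h. For a 0400 draw to lie 5–8 h after a dose, that dose must be given between 2000 (4 − 8 h) and 2300 (4 − 5 h).

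**Urine: where does 1000–1400 fall?**
- Days with a 1200 dose, sample before it: 10–12 h after the 0000 dose.
- Days with a 1200 dose, sample after it: 0–2 h after the 1200 dose.
- Relative to the 1200 dose, allowing for dosing tolerance: 10 − 12.5 = −2.5 h to 14 − 11.5 = +2.5 h.
- Final Tuesday, with no further dose: 10–14 h after dose 14.

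The midpoints between doses are 0600 and 1800 (6 h after a dose). The window never includes either.

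**Day labels.** If the starting Tuesday is Day 1, Day 7 is the following Monday and the following Tuesday is Day 8. The plan calls that Tuesday Day 7, so the two labels cannot both stand.

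**Proposed times.**
- Urine at 0600 ±2 h is 4–8 h after the 0000 dose. From the starting Tuesday to the following Tuesday that is 8 samples, the same as Days 0 to 7 now.
- With doses at 1000 and 2200, dose 14 is 156 h after Tuesday 1000, at Monday 2200. The 0400 draw is then 6 h later (5.5–6.5 h). Urine at 0400 ±2 h is 4–8 h after the 2200 dose.

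**The case against.** The strongest reply is that this amounts to one inaccurate rationale and one inaccurate parenthesis. Several parts of that reply stand:
- The nominal 4 h lag is the same in all three arms, so the between-dose comparison is not biased.
- No endpoint is defined as a peak; Aim 3 asks only for a level above 37 µmol/L.
- The 5–8 h figure comes from a cited study in healthy subjects that cannot be checked here, and section 4.0 says the enteral half-life is unstudied. The error may lie in the 5–8 h figure rather than in the schedule.
- If Day 7 is the following Tuesday, the final urine does not straddle a dose. The mixing then affects only the intermediate days, which are graphed and not tested.
- Nothing in the documents shows that 0600 urine reflects nitric oxide production better than noon urine.
- Dose and draw times may be retrievable from the medical record, though the plan does not say they will be used.

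The reply does not remove the point. Deleting the two phrases would make the text consistent but would leave the urine window centred on a dose, when the plan says it wants a sample between doses.

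Two stronger readings are tempting, and the documents do not support either:
- A reader might take "supplementation will be discontinued (last dose Monday PM") to mean Monday noon, which would give a 16 h lag. Fourteen doses from Tuesday 1200 end at midnight, and the plan itself pairs the 0000 dose with the 0400 draw.
- A reader might infer from "If patients complete 12/14 doses of the treatment, they will be analyzed in the treatment arm" that lags of 16 h or 28 h will enter the analysis and inflate the SD. The rule allows missed doses, but no rate is given and nothing suggests the last doses would be the ones missed. Section 6.0 has bedside nurses give every dose. Putting a size on the effect would need assumed enteral kinetics and a baseline level that the plan does not state.

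**Conclusion.** Both mismatches are real and follow from the plan's own clock times. Plasma is sampled 4 h (3.5–4.5 h) after the midnight dose, 0.5–1.5 h short of the window used to justify the schedule. Urine is never mid-interval: about 10–12 h or 0–2 h post-dose on dosing days, and about 10–14 h on the final Tuesday.

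The consequence is limited. The urine mix adds noise of a size that cannot be computed from the documents, and the plasma level cannot be called a peak on the plan's own terms. There is no bias in the between-dose ANOVA, and no sample size or power figure changes. The documents show an internal mismatch; they do not show that 4 h is a poor time to measure citrulline.

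The conclusion assumes dosing from Tuesday 1200 and a draw at the stated 0400. The point deserves more than a wording change because a small shift in times would let the urinary part of the primary outcome and the single on-treatment plasma sample do what the plan says they do.

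**What to change.** **Urine.** Collect at 0600 ±2 h each day. Take the first sample on the starting Tuesday before the first dose and the last on the following Tuesday, 6 h after dose 14. The number of samples stays at 8.

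**Labels.** Use one set for blood and urine: the starting Tuesday before dosing is Day 0, and the following Tuesday is Day 7.

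**Plasma.** Choose one of two options.
- Keep the dosing times, delete the peak claim, and describe the Day 7 level and the >37 µmol/L result as about 4 h post-dose, using recorded dose and draw times.
- If a 5–8 h level is wanted, dose at 1000 and 2200 so that the 0400 draw is 6 h (5.5–6.5 h) post-dose, and collect urine at 0400 ±2 h.

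**Cost.** Protocol wording, a changed nursing time for urine, and recording of dose and sample clock times. The second plasma option also changes dosing and dispensing times, and it aims at a window that the documents do not let us verify. Neither option needs an extra sample or procedure.
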